5.1.1. Visit Windows

As subjects do not always adhere to the protocol visit schedule, the following rules are applied to assign actual visits to analysis visits. Listed below are the visit windows for analysis and the target days for each visit. The reference day is Re-treatment Day 1 (for definition see section 5.1.3). If a subject has two or more actual visits in one visit window, the visit closest to the target day will be used as the protocol visit for that visit window. Additional or unscheduled visits will not be used in the summaries or analyses, but they can be used for determination of clinically important endpoints. If two actual visits are equidistant from the target day within a visit window, the later visit will be used.

Study visits of Study Parts 1, 2 and 3 taken place before re-treatment with guselkumab has been started will not be re-assigned to visit windows as they will not be included in tabulation; however, the (negative) relative day will be computed to be displayed in the individual data listings.

All assignments will be made in chronological order. Once a visit date is assigned to a visit window, it will no longer be used for a later time point except for the endpoint. Listed below in Table 2 are the visit windows and the target days for each visit of the Re-treatment phase.

Table 2 – Visit Windows for Analysis

Parameter	Analysis Period	Scheduled Visit	Time Interval (Label on output)	Time Interval (Day) *	Target Time Point (Day)
All	Re-trt	R0	Week R0	Not applicable #	1
		R8	Week R8	20 to 85	57
		R16	Week R16	86 to 127	113
		R24	Week R24	> 127	169
		R28	Week R28 (SFU)	Not applicable&	197

* Relative to Re-treatment Day 1. Time intervals for analysis are wider than the visit windows allowed per CSP.

In some subjects, the first re-treatment dose was given at an unscheduled visit after the R0 visit. For these, the R0 visit will have a negative relative day.

& No visit window is defined for the safety follow-up visit as no efficacy data are obtained at this visit.

If there are site visits outside of the defined windows above, final decisions on the allocation of the actual visit to an earlier or later planned visit or whether the data will not be included in the analysis will be made during the Data Review or Dry Run Meeting.

Table 2 above shows visit windows for visits during the Re-treatment phase only. In addition, for PASI, DLQI and BSA, up to five pre-R0 visits will be selected for tabulation according to the 12-week visit schedule: Visit R-1 (“R minus 1”) is the regular visit before R0, R-2 is the regular visit before R-1, R-3 is the regular visit before R-2, R-4 is the regular visit before R-3, and R-5 is the regular visit before R-4. For analysis groups I and II, only visit R-1 (lying in Study Part 2) will be

used. For the analysis groups III to V, the earliest visit to be used is the week 68 visit (start of the Drug withdrawal phase). For this analysis, if a score value for a visit is missing it will not be imputed and the subject will not provide data for the respective R-x visit.

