Re-treatment visits are to be conducted within ± 7 calendar days; please prospectively contact the Sponsor for further instructions if it is anticipated that a visit may fall outside this window. In the event of early discontinuation of study agent, these assessments should be conducted at the time of discontinuation of study agent (ETV). After ETV, safety follow-up should be conducted for 12 weeks after the last administration of study drug. Subjects who discontinue study agent may or may not continue in the study depending on the reason for discontinuation of study agent; refer to Section 10.2 for further details.

***)**: Subjects (SRe) with PASI score >5 at any visit in Study Part 2 or 3, or a PASI score ≥ 3 at week 68 will receive guselkumab 100 mg q8w for further 3 administrations (at that visit = re-treatment weeks 0, 8 and 16) and study termination after 28 weeks (Safety-Follow Up visit)

- a. All study procedures and evaluations are to be completed before study drug injection. Assessments for subjects who discontinue study agent administration or withdraw from the study are described in Section 10.2 and 10.3, respectively.
- b. Subjects will receive guselkumab 100 mg q8w for further 3 administrations (re-treatment weeks 0, 8 and 16).
- c. Women of childbearing potential must have a negative urine pregnancy test result at all study visits before study treatment drug administration.
- d. Performed by the subject (PRO) before any tests, procedures, or other evaluations (eg, PASI, affected BSA or NAPPA-CLIN) are performed for that visit.
- e. TLSS for the selected target lesion will be recorded at each biopsy collection time.
- f. Photo-documentation will be done standardized and professionally at few selected sites equipped with an appropriate photography laboratory (described in Photo-documentation manual).
- g. All blood samples must be collected before study drug administration at visits when a study drug administration is scheduled. Details will be provided in the Laboratory Manual.
- h. Laboratory assessments can be non-fasting and are listed in Section 9.6.
- i. One additional blood sample for pharmacokinetic and serum biomarker assessments will be taken at the time when the subject loses control of disease (defined as PASI score >5 at any visit during Study Parts 2 or 3, or PASI ≥ 3 at week 68). However at R0, PK-samples will only be taken for Study Part 2d (ie, not for Study Part 3c).

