5.1.8. Missing Data Imputation

Data of efficacy endpoints from subjects who started a protocol-prohibited medication/therapy during the study that could improve psoriasis will be set to 'missing' from that point onward. If the prohibited medication was stopped and the stop date is before the R0 visit, any efficacy data observed on or after the R0 visit will be used for analysis. The protocol-prohibited medications/therapies are listed in section 8.1 of the CSP. For the statistical analysis of the Re-treatment phase, protocol prohibited medication/therapy will be identified in the SDTM DV domain as DVDECOD='Received a disallowed concomitant treatment'.

After the rule for handling of protocol-prohibited medication/therapy is applied, missing data will be handled as follows:

- Non-responder imputation for binary efficacy endpoints will be applied for subjects with missing data within a given visit window.
- Last Observation Carried Forward (LOCF) imputation for continuous efficacy endpoints will be applied for subjects with missing data in the Re-treatment phase. Only the visits R8, R16, and R24, or any unscheduled visit after R0, will be considered as the LOCF value.
 - This approach implies that a separate "endpoint" visit will be calculated that gets the imputed value, thus leaving the observed value as it is, if data are summarized descriptively only.
- Time-to-event analyses of binary endpoints will be performed after the rule for handling of protocol-prohibited medication/therapy is applied (missing data will not be replaced for time-to-event analyses).

An 'observed cases analysis' for all binary and continuous endpoints in the Re-treatment phase without any imputation of missing data (ie, also not set to missing once protocol-prohibited medication/therapy is started) will also be done. These analyses will provide only descriptive statistical results (see section 5.6).

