5.5.3. Analysis Methods

5.5.3.1. Psoriasis Area and Severity Index (PASI)

- Proportion of subjects who regain control of disease (PASI <3) 24 weeks after start of re-treatment

The proportion of subjects showing a PASI value <3 within the R24 visit window will be displayed in a frequency table providing the number and percentage of subjects per analysis group and overall (NRI and OC analysis). For all proportions, unstratified two-sided 95% confidence intervals (CIs) according to Clopper-Pearson will be calculated. Graphical presentation will be done by means of bar charts.

Details on handling of missing data are described in section 5.1.8. For the analysis groups III to V (total only), subgroup analyses will be performed as specified in section 5.8.8. Subgroups will be compared exploratorily for the NRI analysis using the Chi-square test (without covariate) to test the difference between two subgroups. The 95% confidence interval for the difference will be calculated based on the Wald statistic. Counts and percentages for subjects responding to treatment, along with odds ratio (OR), relative risk (RR) and risk difference (RD), 95% confidence intervals and the nominal (not adjusted for multiplicity) p-value for the factor effect 'subgroup' will be provided. Graphical presentation will be done by means of bar charts.

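### The week R24 window opens on day 128, so PASI values nearer to R16 can count as the week-24 re-treatment outcome

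*SAP*

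**What the plan says.** Table 2 in Section 5.1.1 of the Re-treatment SAP counts days from the first re-treatment dose (Day 1). Its three efficacy rows, each giving interval and then target day, are "R8 Week R8 20 to 85 57", "R16 Week R16 86 to 127 113" and "R24 Week R24 > 127 169". The footnote adds "Time intervals for analysis are wider than the visit windows allowed per CSP". The protocol's own rule, in the notes to the re-treatment Time and Events Schedule, is "Re-treatment visits are to be conducted within ± 7 calendar days".

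The endpoint is read from this window. Section 5.5.3.1 tabulates "The proportion of subjects showing a PASI value <3 within the R24 visit window". Section 5.1.8 limits imputation accordingly: "Non-responder imputation for binary efficacy endpoints will be applied for subjects with missing data within a given visit window".

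Section 5.1.1 also has three provisions that bear on the point:

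- When several visits share a window, the one nearest the target day is used.
- Additional or unscheduled visits are left out of the summaries.
- Visits that fall outside every window are settled at the Data Review or Dry Run Meeting.

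R28 has no window because no efficacy data are collected there.

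**The concern.** The R8/R16 border lies exactly halfway between its two targets, but the R16/R24 border does not. It sits two weeks on the R16 side of the halfway point, and the SAP gives no reason. Two things follow.

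- **No later PASI.** A subject has a late R16 visit, or stops and has an early-termination assessment, on days 128 to 140, and is not seen again for efficacy. The R24 window then contains a value, so imputation is not triggered, and a PASI below 3 is reported as control regained at week 24. The protocol schedules assessments before the injection, so a late R16 value of this kind would predate the dose given at that visit.
- **R24 visit also held.** Both visits fall in the R24 window. The one nearer day 169 is kept, the R16 value is dropped, and R16 becomes an imputed non-response in the by-visit response tables of Section 5.6.1, although it was observed.

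Regaining PASI below 3 at 24 weeks is the one protocol endpoint formulated specifically for re-treatment. The other R24 response proportions (PASI 0, ≤1 and ≤5; DLQI 0/1 and <5) use the same window.

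**Working it through.** **Inputs.** Windows and targets come from Re-treatment SAP Table 2. The ±7-day rule comes from the protocol's re-treatment schedule. The numbers re-treated come from the Overall safety SAP, Section 4.5: 227 after withdrawal, plus 9 without a withdrawal phase, giving 236.

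**Reproducing the targets.** Target day = 7 × week + 1, because there is no Day 0:

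- R8: 7 × 8 + 1 = 57
- R16: 7 × 16 + 1 = 113
- R24: 7 × 24 + 1 = 169
- R28: 7 × 28 + 1 = 197

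All four match Table 2.

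**Borders against midpoints.**

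| Pair | Midpoint of targets | Last day of earlier window | Gap |
|---|---|---|---|
| R8/R16 | (57 + 113)/2 = 85 | 85 | 0 days |
| R16/R24 | (113 + 169)/2 = 141 | 127 | 14 days |

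**Width of the R24 window on the early side.** It opens 169 − 128 = 41 days before target. The protocol's earliest R24 day is 169 − 7 = 162, so the window opens 162 − 128 = 34 days before that.

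**Days nearer to R16.** Day 128 is 15 days from R16 and 41 from R24. Day 140 is 27 from R16 and 29 from R24. Day 141 is 28 from both. So 13 days (128 to 140) are strictly nearer to R16 but are filed as R24.

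**Do the existing rules catch this?**

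- *Nearest visit:* this needs a second visit in the window. Days 128 to 140 lie 41 to 29 days from target, so an R24 visit within 28 days of target always wins. A subject with no R24 visit is not helped.
- *Meeting review:* this covers only visits outside the windows, and no visit after day 127 can be outside.
- *Unscheduled visits excluded:* a late scheduled R16 visit is not unscheduled.

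**Example of the second effect.** R16 is held on day 130 and R24 on day 169. Both fall after day 127, so day 169 is kept. Days 86 to 127 hold nothing, and R16 is imputed as non-response.

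**Scale.** One subject moved from imputed non-responder to responder shifts the R24 proportion by 100/227 = 0.44 or 100/236 = 0.42 percentage points. The number affected is not in the documents, so the following is an assumed range:

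| Reclassified subjects with PASI <3 | N = 227 | N = 236 |
|---|---|---|
| 1 | 0.44 | 0.42 |
| 5 | 2.2 | 2.1 |
| 10 | 4.4 | 4.2 |
| 20 | 8.8 | 8.5 |

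Each subject weighs more within a single analysis group or subgroup.

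**The case against.** The strongest reply is that the affected subjects should be few. The R16 route needs a visit at least 15 days late, against a protocol tolerance of 7, and then no R24 visit. The early-termination route is less certain: the protocol asks for the assessments at discontinuation, but the re-treatment schedule has no column for that visit, and the SAP does not say whether it counts as an additional visit. Subjects who switch to a prohibited psoriasis therapy are already covered, because Section 5.1.8 sets their later efficacy data to missing. All of this stands, and it limits the weight of the point.

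A second reply is that no SAP states a midpoint rule, and that day 127 is the R16 target plus 14, the half-width the Part 3 SAP uses for its 8-weekly visits (week 36: days 239 to 267, target 253). That could explain where R16 closes, but not why R24 opens the next day. In the Part 3 SAP, week 44 starts only at day 295 (target 309), so days 268 to 294 belong to neither visit.

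A reader might also infer from the missing upper limit that any PASI long after R24, even one taken on commercial guselkumab, counts as the week-24 result. The documents do not support that. No PASI is scheduled after the R24 visit, R28 has none, and unscheduled visits are excluded. Commercial guselkumab may be continued only from the R24 visit itself. The open end therefore mainly admits a delayed but genuine R24 assessment. The Part 3 SAP likewise states that its final visits have no upper border.

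**Conclusion.** The early edge of the R24 window is misplaced. At R24, under non-responder imputation, the error for a subject with no later PASI can only raise the response rate: a PASI of 3 or more is non-response either way, and only a value below 3 changes the result. At R16 the effect on subjects seen at both visits runs the other way, because an observed response can become an imputed failure. The window therefore does not favour re-treatment throughout.

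The size is about 0.4 percentage points per reclassified subject with PASI below 3, taking 227 to 236 as the denominator. The total cannot be stated without the visit dates. The endpoint is an other secondary endpoint, analysed descriptively in an open-label phase, and the confirmatory non-inferiority result at week 68 does not depend on it. The point is worth correcting because the correction is cheap. The documents do not show that the reported proportion would change materially.

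**What to change.** In Table 2, set R16 to days 86 to 141 and start R24 at day 142. This places the border at the midpoint and gives the equidistant day to the earlier visit, as the R8/R16 border does with day 85. A subject with no PASI from day 142 onward is then a non-responder at R24. Report the present window (all days after 127) as a sensitivity analysis, with the number of subjects whose R24 status differs.

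Keep the open upper end so that a delayed scheduled R24 visit still counts. A cap, for example at day 197, would turn some observed responses into failures and should be examined only as a sensitivity analysis. State also whether an early-termination assessment may be assigned to a window.

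The cost is two changed limits in Table 2, a rerun of the re-treatment tables, and an entry in the SAP's list of changes, since the existing windows were set before the first interim re-treatment analysis. The downside is possibly a few more non-responders at R24.

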5.1.2. Pooling Algorithm for Analysis Centers

No pooling of centers will be performed.

5.1.3. Study Day and Relative Day

Study Day 1 or Day 1 refers to the start of the first study agent administration within Study Part 1. However, for the analysis of the Re-treatment phase, the efficacy and safety assessments at all visits, including those of Study Parts 1, 2, and 3, will be assigned a day relative to the date re-treatment with guselkumab started (first dose of Re-treatment phase).

Hence, the relative day for a visit within the current analysis is defined as:

- Visit date – Date of Re-treatment Day 1 + 1, if visit date is \geq start date of re-treatment
- Visit date – Date of Re-treatment Day 1, if visit date is $<$ start date of re-treatment.

There is no 'Day 0'.

5.1.4. Baseline and Endpoint

Baseline for the Re-treatment phase is defined as the observation made at the R0 visit.

Endpoint for the Re-treatment phase is defined as the last available post-baseline result within the analysis period after the R0 visit. Results obtained at unscheduled visits are included in this definition and will be considered as the endpoint value if the unscheduled visit result is the last post-baseline result available within the analysis period for the Re-treatment phase.

5.1.5. Imputation Rules for Missing AE Date/Time of Onset/Resolution

Partial onset dates of adverse events (AEs) will be imputed as follows:

- If the onset date of an AE is missing day only, it will be set to:
 - First day of the month that the AE occurred, if month/year of the onset of AE is different than the month/year of the study agent start
 - Day of study agent start, if the month/year of the onset of AE is the same as month/year of the study agent start date and month/year of the AE resolution date is different
 - Day of study agent start or day of AE resolution date, whichever is earliest, if month/year of the onset of AE and month/year of the study agent start date and month/year of the AE resolution date are same.
- If the onset date of an AE is missing both day and month, it will be set to the earliest of:
 - January 1 of the year of onset, as long as this date is on or after the study agent start date
 - Month and day of the [study agent start date], if this date is the same year that the AE occurred
 - Last day of the year if the year of the AE onset is prior to the year of the [study agent start date],
 - The AE resolution date.
- Completely missing onset dates will not be imputed.

Partial AE resolution dates not marked as ongoing will be imputed as follows:

- If the resolution date of an adverse event is missing day only, it will be set to the earliest of the last day of the month of occurrence of resolution or the day of the date of death, if the death occurred in that month.
- If the resolution date of an adverse event is missing both day and month, it will be set to the earliest of December 31 of the year or the day and month of the date of death, if the death occurred in that year.
- Completely missing resolution dates will not be imputed.

5.1.6. Treatment Failure Criteria

No treatment failure criteria are defined for the analysis of the Re-treatment phase.

5.1.7. Treatment Failure Rules

Not applicable as there are no treatment failure criteria.

5.1.8. Missing Data Imputation

Data of efficacy endpoints from subjects who started a protocol-prohibited medication/therapy during the study that could improve psoriasis will be set to 'missing' from that point onward. If the prohibited medication was stopped and the stop date is before the R0 visit, any efficacy data observed on or after the R0 visit will be used for analysis. The protocol-prohibited medications/therapies are listed in section 8.1 of the CSP. For the statistical analysis of the Re-treatment phase, protocol prohibited medication/therapy will be identified in the SDTM DV domain as DVDECOD='Received a disallowed concomitant treatment'.

After the rule for handling of protocol-prohibited medication/therapy is applied, missing data will be handled as follows:

- Non-responder imputation for binary efficacy endpoints will be applied for subjects with missing data within a given visit window.
- Last Observation Carried Forward (LOCF) imputation for continuous efficacy endpoints will be applied for subjects with missing data in the Re-treatment phase. Only the visits R8, R16, and R24, or any unscheduled visit after R0, will be considered as the LOCF value.
 - This approach implies that a separate "endpoint" visit will be calculated that gets the imputed value, thus leaving the observed value as it is, if data are summarized descriptively only.
- Time-to-event analyses of binary endpoints will be performed after the rule for handling of protocol-prohibited medication/therapy is applied (missing data will not be replaced for time-to-event analyses).

An 'observed cases analysis' for all binary and continuous endpoints in the Re-treatment phase without any imputation of missing data (ie, also not set to missing once protocol-prohibited medication/therapy is started) will also be done. These analyses will provide only descriptive statistical results (see section 5.6).

5.2. Participant Dispositions

The number of subjects in the following disposition categories will be summarized by analysis group (see Section 5.0) and overall:

- Subjects who started re-treatment #
- Subjects who completed the Re-treatment phase
- Subjects who discontinued the Re-treatment phase prematurely
- Reasons for termination of study within the Re-treatment phase.

The first interim analysis will include all subjects who started re-treatment at the latest by the week 116 visit, the second (optional) interim analysis all subjects who started re-treatment at the latest by the week 164 visit, and the final analysis all subjects who started re-treatment at the latest by the week 220 visit.

5.3. Primary Endpoint(s) Analysis

Not applicable for the re-treatment analysis.

5.3.1. Definition of Endpoint(s)

Not applicable for the re-treatment analysis.

5.3.2. Estimand

Not applicable for the re-treatment analysis.

5.3.3. Analysis Methods

Not applicable for the re-treatment analysis.

5.4. Major Secondary Endpoint(s) Analysis

Not applicable for the re-treatment analysis.

5.4.1. Definition of Endpoint(s)

Not applicable for the re-treatment analysis.

5.4.2. Estimand(s)

Not applicable for the re-treatment analysis.

5.4.3. Analysis Methods

Not applicable for the re-treatment analysis.

5.5. Other Secondary Endpoint(s)

Statistical analyses will be descriptive and exploratory only. They will be performed for the Intent-to-treat analysis set and, if requested, the Per-protocol analysis set. Details on handling of missing data are described in section 5.1.8.

Other secondary endpoints of this study to be evaluated for the Re-treatment phase are:

- Proportion of subjects who were re-treated due to loss of disease control (PASI >5) and regain control of disease (PASI <3) 24 weeks after start of re-treatment.

